9.3. Vital Sign Measurements

Vital signs, including blood pressure (mmHg), heart rate (BEATS/MIN), respiration (BREATHS/MIN), and body temperature ($^{\circ}$ C) will be obtained with the patient in a supine or seated position after resting for approximately 5 minutes.

Observed values and changes from baseline will be provided for vital signs parameters using descriptive statistics by treatment group and scheduled visit.

All vital sign measurements will be presented in a listing.

9.4. Electrocardiogram

Twelve-lead ECGs will be performed to calculate the heart rate (HR, BEATS/MIN), PR Interval (msec), QRS Duration (msec), QT Interval (msec), and QT interval Fridericia correction (QTcF, msec). The ECGs will be obtained with the patient in supine position. All standard 12 lead ECGs will be recorded and analysed locally at the site by the investigator.

Observed values and changes from baseline will be provided for ECG parameters using descriptive statistics by treatment group and scheduled visit.

The proportion of patients with a clinically significant abnormal ECG result will be provided by treatment group and scheduled visit.

A summary of shifts in 12-lead ECG abnormalities from baseline will be provided by scheduled visits.

ECG results for all patients will be presented in a listing.

9.5. Physical Examination

A complete physical examination including assessments of the head, eyes, ears, nose, throat, skin, neck (including thyroid), lungs, cardiovascular system, abdomen, lymph nodes, and extremities will be obtained at screening. A physical examination including updates since the screening visit with focus on previously noted abnormalities in organ systems, including skin and hair, will be completed at time points specified in Schedule of Events.

Physical examination data will be summarised by treatment group and body system with number and percentage of patients.

Physical examination results for all patients will be presented in a listing.

10. Interim Analysis

A data safety monitoring board (DSMB) will review unblinded safety data throughout the study and make recommendations as appropriate. Further details are specified in the DSMB charter.

11. Changes in the Planned Analysis

The changes for the statistical analyses from the protocol to this SAP are stated below:

1. The analysis set to be used for perioperative endpoints (Circulatory Arrest Time, Surgery-related Complications, Surgical Evaluation of Specimen, PEA hospital length of stay, PEA ICU length of stay, Time on mechanical ventilation, In-hospital mortality) have been updated to PEA set only, with the consideration that these endpoints are peri-PEA surgery related endpoints and it makes more sense to narrow down the patients to those who have undergone PEA surgery only.
2. The analysis sets to be used for postoperative endpoints (Percent Change in PVR from baseline to Visit 4, Composite clinical endpoint from baseline to Visit 4, NT-proBNP, cardiac output, cardiac index, mRAP, mPAP, PAWP change from baseline to Visit 4, Functional class at Visit 4, All-cause death, Need for PAH-targeted postoperative therapy at Visit 4) have been updated to PEA set and PPS, with the consideration that the endpoints are post-PEA surgery endpoints, and it makes more sense to restrict the analysis to patients who undergone PEA surgery; PPS will be used since those per-protocol patients need to be considered as a complementary analysis set.
3. The analysis defined in the protocol “For laboratory data, the proportion of patients with clinically significant abnormal values as reported by the investigator will be provided by laboratory parameter, dose cohort, and scheduled visit.” Will be removed since it is confirmed by central labs that the data on ‘clinically significant/non-clinically significant’ will not be obtained.
4. The observation period for composite endpoints as now defined in section 8.2.2 has been changed to ‘from randomisation to Visit 4’ instead of ‘from PEA to Visit 4’ since it is of more interest to investigate the endpoints from randomization;
5. The exploratory endpoint ‘Need for PAH-targeted postoperative therapy at the 6-month visit (Visit 4)’ in the protocol has been changed to ‘Need for PAH targeted postoperative therapy from immediately after PEA to Visit 4’ since it is of more interest to see if PAH targeted therapy occurs from PEA till Visit 4.

The surgical evaluation of specimen is from perioperative measurement (Visit 3), according to the new text of Appendix 1 in Protocol Amendment 1.

12. References

1. Investigator's Brochure V18.0 23Feb18, Section "5.4.2 Exposure Information".

13. Appendices

13.1. Schedule of Events

	Visit 0 Pretreatment / Screening	Visit 1 Randomisation & baseline visit	Visit 2 RHC visit (Pre- PEA)	Visit 3 Post-PEA	Visit 4 Follow-up visit incl. RHC
Time frame	Day -89 to 1	Day 1	Day 90+30	Day 96 ^a	Day 276±10
Activity / Observation					
Written informed consent	X				
Inclusion/exclusion criteria review	X	(X) ^b			
Assessment of current tobacco use	X				
Demographic data including height and weight	X				
HIV test	(X) ^b	X			
Medical and treatment history	X	X			
Physical examination including WHO functional class	X	X	X	X	X
Vital sign measurements	X	X	X	X	X
Clinical laboratory assessments (haematology, clinical chemistry, and urinalysis)	(X) ^b	X	X	X	X
NT-proBNP measurement		X	X		X
Haemodynamics incl. PVR, mRAP, mPAP, cardiac index, pulmonary artery wedge pressure measurement	X ^c		X		X
12-lead ECG		X	X		X
Pregnancy test (if applicable) ^d	X	X	X		X
Randomisation/treatment assignment		X			
Administration of double-blind study drugs ^e		X	X		
Provision of patient diary	X				

	Visit 0 Pretreatment / Screening	Visit 1 Randomisation & baseline visit	Visit 2 RHC visit (Pre- PEA)	Visit 3 Post-PEA	Visit 4 Follow-up visit incl. RHC
Time frame	Day -89 to 1	Day 1	Day 90+30	Day 96 ^a	Day 276±10
Activity / Observation					
Perioperative assessment (circulatory arrest time, surgery-related complications)			X ^f		
Surgical evaluation of specimen ^g				X ^g	
Hospital and ICU length of stay				X	
Time on mechanical ventilation				X	
PAH-targeted therapy assessment	X	X	X	X	X
PH-related hospitalisation		X	X	X	X
Adverse event monitoring	X	X	X	X	X
Concomitant medications		X	X	X	X
Return of patient diary				X	
Return of study drug				X	
Telephone call			X ^h		X ⁱ
Patient compliance check (study procedures and study drug)		X	X	X	X

Abbreviations: ECG, electrocardiogram; HIV, human immunodeficiency virus; ICU, intensive care unit; incl., including; mPAP, mean pulmonary arterial pressure; mRAP, mean right atrial pressure; NT-proBNP, N-terminal pro-B-type natriuretic peptide; PAH, pulmonary arterial hypertension; PEA, pulmonary endarterectomy; PH, pulmonary hypertension; PVR, pulmonary vascular resistance; RHC, right heart catheterisation; WHO, World Health Organization

^a The PEA will be conducted by the principal surgeon of the site within a week of RHC.

^b When laboratory analysis results are required/available (see Protocol Section 4.2)

^c Patients must have undergone an RHC ≤ 180 days before Visit 1. This procedure is considered a prerequisite for participation and not part of the study itself. If it was performed at a referring centre, it is at the investigators' discretion based on the quality of the RHC data and the experience of the referring site to enroll the patient.

^d Urine dipstick or serum pregnancy testing will be performed at Visit 0. Serum testing will be performed for all other applicable visits.

^e The study drug will be initiated no later than 180 days after RHC. At Visit 2, RHC will be performed within 90 days of the initiation of treatment per site procedures no more than 1 week prior to PEA.

^f Perioperative measures.

^g Difficulty to withdraw obstructive material, ease of dissection plane (easier than normal, normal, or more difficult than normal), completeness of disease clearance (better than expected, as expected, or worse than expected).

^h The treating physician should contact the patient at least once by telephone during treatment period.

ⁱ The treating physician should contact the patient during follow-up at 186±10 day by telephone, where questions related to patient's well-being adverse events can be asked.

13.2. World Health Organization Classification for Patients With Pulmonary Arterial Hypertension

Functional Class	Symptomatic Profile
I	Patients with pulmonary hypertension but without resulting limitation of physical activity. Ordinary physical activity does not cause dyspnoea or fatigue, chest pain, or near syncope
II	Patients with pulmonary hypertension resulting in slight limitation of physical activity. They are comfortable at rest. Ordinary physical activity causes undue dyspnoea or fatigue, chest pain, or near syncope
III	Patients with pulmonary hypertension resulting in marked limitation of physical activity. They are comfortable at rest. Less than ordinary activity causes undue dyspnoea or fatigue, chest pain, or near syncope
IV	Patients with pulmonary hypertension with inability to carry out any physical activity without symptoms. These patients manifest signs of right heart failure. Dyspnoea and/or fatigue may even be present at rest. Discomfort is increased by any physical activity

13.3. Surgery-related complications

Surgery-related complications are defined as the following:

- Bleeding and/or blood loss >1 L in 12 hours
- Airway bleed with need for extracorporeal membrane oxygenation
- Any use of extracorporeal membrane oxygenation for respiratory or haemodynamic support, specified as veno-venous or veno-arterial
- Prolonged ventilation >96 hours
- Need for tracheostomy
- Need for drainage of pericardial effusion
- Neurological complications, ie, stroke, cerebral, subdural bleeding
- Reintubation or noninvasive ventilation for reperfusion response
- Haemoptysis requiring any intervention
- Renal failure requiring dialysis
- Wound infections
- Pneumonia
- Prolonged need for inotropic support (≥ 5 days)

13.4. Adverse Events/ Prior or Concomitant Medications Date Imputation

Incomplete Start Date:

Missing day and month

- If the year is the same as the first dose of study drug, then the date of the first dose of study drug will be assigned to the missing fields.
- If the year is before the year of first dose of study drug, then December 31 will be assigned to the missing fields.
- If the year is after the year of first dose of study drug, then January 1 will be assigned to the missing fields.

Missing day only

- If the year is the same as the year of the first dose of study drug
 - If the month is before the month of the first dose of study drug, then the last day of the month will be assigned to the missing day.
 - If the month is the same as the month of the first dose of study drug, then the day of the first dose of study drug will be assigned to the missing day.
 - If the month is after the month of the first dose of study drug, then “01” will be assigned to the missing day.
- If the year is before the year of the first dose of study drug, then the last day of the month will be assigned to the missing day.
- If the year is after the year of the first dose of study drug, then “01” will be assigned to the missing day.

If year is missing, start date will not be imputed. If the end date is complete, and the imputed start date is after the end date, the start date will be imputed by the end date.

Incomplete End Date:

Missing day and month

- December 31 will be assigned to the missing fields.

Missing day only

- The last day of the month will be assigned to the missing day.

If imputed end date is later than death date if available, the death date will be used as the imputed end date.

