3.2.3. Exploratory Efficacy Endpoints

The exploratory efficacy endpoints are mentioned below.

1. NT-proBNP measurement concentration change from baseline at the preoperative visit (Visit 2) and at 6 months after PEA (Visit 4)
2. Cardiac index change from baseline at the preoperative visit (Visit 2) and at 6 months after PEA (Visit 4)
3. Mean right atrial pressure (mRAP) change from baseline at the preoperative visit (Visit 2) and at 6 months after PEA (Visit 4)
4. Mean pulmonary arterial pressure (mPAP) change from baseline at the preoperative visit (Visit 2) and at 6 months after PEA (Visit 4)
5. Pulmonary artery wedge pressure (PAWP) change from baseline at the preoperative visit (Visit 2) and at 6 months after PEA (Visit 4)
6. Hospital length of stay

The hospital length of stay in days will be derived from the first date when the patient is hospitalised for PEA until the date when the patient is discharged from the hospital.

7. ICU length of stay in days
8. Time on mechanical ventilation, in hours, from start of ICU stay until end of mechanical ventilation
9. In-hospital mortality

Only deaths that happen on or after PEA but before discharge from the hospital will be included.

10. Functional class at the preoperative visit (Visit 2) and at 6 months after PEA (Visit 4)
11. Need for PAH-targeted postoperative therapy from immediately after PEA to the 6-month visit (Visit 4)

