- When frequency counts are presented, the percentage will be suppressed when the count is zero in order to draw attention to the non-zero counts. A row denoted “Missing” will be included in count tabulations where specified on the shells to account for dropouts and missing values. Percentages will be based on the total number of patients in the respective analysis set unless otherwise specified.
- Unless otherwise specified, statistical tests will be 2-sided and performed using a 5% significance level, leading to 95% (2 sided) confidence intervals (CIs). Modelling techniques will be used in an exploratory sense. No adjustments for multiplicity are made.
- Partial dates will be imputed based on the rules specified in Appendix 13.4.
- All laboratory data will be reported by using the International System of Units.
- Unless otherwise specified, the baseline will be defined as the last valid assessment, including assessments from the unscheduled visit, prior to the study drug administration.
- A Visit 2 assessment is considered as valid only when the assessment is completed within 7 days prior to PEA. For assessments at Visit 4, the nominal visit collected in electronic case report form (eCRF) will be used in the analysis. This rule is applicable to all endpoints derived by the visit.
- By-patient listings will be created for each eCRF module for all screened patients. Patients will be identified in the listings by patient number. If data are to be summarised by visit, the visit name collected on the eCRF page will be used.
- All analyses will be conducted using SAS® software Version 9.3 or later (SAS Institute Inc, Cary, North Carolina).

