4.3.3. Per Protocol Set (PPS)

The PPS will consist of all ITT patients who fulfil all inclusion/exclusion criteria, have at least 80% overall dose compliance with study drug, have not taken any prohibited medication, have no significant protocol deviations, have valid PVR assessments at baseline (from patient history) and Visit 2, and undergo PEA as planned. All analyses using the PPS will group patients according to treatment actually received. A blind review of data will identify which patients will be included in the PPS.

The PPS will be used in the primary and secondary efficacy analyses as supportive analyses.

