4.4. Subgroups

Safety analyses (see Section 9.1) will be performed for the following subgroups for AEs occurring between V0 and V2:

- Intake of concomitant DOACs or NOACs being reported during V0 to V2
- Intake of concomitant vitamin K antagonists being reported during V0 to V2
- Intake of concomitant β -blockers being reported during V0 to V2

5. Patient Disposition

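### Partial start dates in SAP 13.4 are anchored only on the first dose, so some post-operative starts can be dated before surgery and enter pre-operative summaries

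*SAP*

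**What the plan says.** SAP Section 4 sends every incomplete date to one place: "Partial dates will be imputed based on the rules specified in Appendix 13.4". Appendix 13.4 then gives these rules for start dates on or after the first-dose month:

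- Day and month missing, first-dose year: the start is set to the first-dose date ("then the date of the first dose of study drug will be assigned to the missing fields").
- Day and month missing, later year: "If the year is after the year of first dose of study drug, then January 1 will be assigned to the missing fields".
- Day only missing, first-dose month: the first-dose day.
- Day only missing, later month or later year: the 1st of the reported month. For the same year the condition reads "If the month is after the month of the first dose of study drug".

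End dates go the other way, to month-end or 31 December. No rule uses the PEA date, a visit date or the last dose.

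Three other parts of the SAP depend on which side of surgery a date falls:

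- Section 4.4 plans safety analyses "for the following subgroups for AEs occurring between V0 and V2", and Section 9.1.7 summarises AEs of special interest for V0-V2 as well as V0-V4.
- Exploratory endpoint 11 (Section 3.2.3) counts PAH-targeted therapy from just after PEA to Visit 4. Section 11, change 5, introduced that window.
- The per-protocol set (Section 4.3.3) admits only patients who "have not taken any prohibited medication".

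**The concern.** A first-dose anchor answers one question: is an AE treatment-emergent? It does not answer whether something happened before or after the operation, and the SAP asks that too.

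Several AEs of special interest (haemorrhage, haemoptysis, hypotension, stroke) are also plausible consequences of surgery. Bleeding, haemoptysis needing intervention and stroke are on the surgery-related complications list in Appendix 13.3. If such an AE is dated to the 1st of the PEA month or to the first dose, a stated rule places it in a summary meant to describe pre-operative time on study drug.

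A PAH drug started after surgery can likewise be dated before PEA. That may affect endpoint 11, or raise a query about prohibited medication when the per-protocol set is reviewed. For true post-PEA starts the imputed date is never later than the true one, so the errors do not cancel.

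**Working it through.** The documents state no figure that depends on this rule and no rate of partial dates. The check is how often the rule, as written, moves a true post-PEA start to before PEA.

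**Inputs.** The rules are those of SAP 13.4. PEA follows the Visit 2 catheterisation by at most a week, and the post-PEA visit is Day 96 (Appendix 13.1). Follow-up is 6 months after PEA, taken as 180 days. Assumptions: first-dose dates are spread evenly over a 365-day year, true starts are spread evenly over the post-PEA window, and day 0 is the day of PEA.

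**Day only missing.** Let PEA fall on day d of a 30-day month and let the true start be e days later. The imputed date is before PEA only if the start is still in the PEA month (d + e ≤ 30) and d is not 1. That leaves d = 2 to 30 − e, a share of (29 − e)/30, or zero once e ≥ 29.

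- Days 0-7: mean e is 3.5, so (29 − 3.5)/30 = 0.85.
- Days 0-30: the shares sum to 435/30 = 14.5, and 14.5/31 = 0.47.
- Days 0-180: 14.5/181 = 0.08.
- Days 31-180: 0.

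**Day and month missing.** The imputed date is before PEA when PEA and the start lie in the same calendar year and PEA is not on 1 January. If that year is the first-dose year, the start becomes the first-dose date. If it is a later year, it becomes 1 January. If PEA is in one year and the start in the next, 1 January is still after PEA. The share is (364 − e)/365.

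- Days 0-30: (364 − 15)/365 = 0.956.
- Days 0-180: (364 − 90)/365 = 0.751.

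**Enumeration over the real calendar**, for every first-dose date in the year. The results are the same with PEA on Day 90, 96 or 127.

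| True start after PEA | Day missing: dated before PEA | Day and month missing: dated before PEA |
|---|---|---|
| Days 0-7 | 85% | 99% |
| Days 0-14 | 74% | 98% |
| Days 0-30 | 48% | 96% |
| Days 0-90 | 16% | 87% |
| Days 0-180 | 8% | 75% |
| Days 31-180 | 0% | 71% |

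**Example.** First dose 10 June, PEA 13 September (Day 96). A start on 16 September with the day missing becomes 1 September, before PEA. A start on 3 October becomes 1 October, still after PEA. With day and month missing, both become 10 June.

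**From before PEA to inside V0-V2.** Visit 2 may precede PEA by up to 7 days, so a date before PEA can still fall after Visit 2. If the window is cut at the Visit 2 date and Visit 2 is 7 days before PEA, the 1st falls inside only for d ≥ 8. The day-only share is then (23 − e)/30.

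- Days 0-7: (23 − 3.5)/30 = 0.65.
- Days 0-30: 276/30 = 9.2, and 9.2/31 = 0.30.
- Days 0-180: 9.2/181 = 0.05.

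With Visit 2 one day before PEA, the shares are those in the table. The part entering V0-V2 is therefore about 65-85% for days 0-7, 30-48% for days 0-30 and 5-8% for days 0-180.

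**The case against.** The strongest reply is that the consequences are narrow, and most of it stands.

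- A reader might infer that any unknown day moves a post-operative event before surgery. It does not. The reported month is kept, so only starts in the PEA month are exposed. Nor is all imputation towards the first dose: end dates move later, and so do starts in a month or year before the first dose.
- A reader might infer that surgical complications will be reported as pre-operative. The complications endpoint (SAP 8.2.3.2, Appendix 13.3) is a predefined list from a perioperative assessment and is not windowed by AE start date. Only parallel AE records are exposed. Patients are in hospital just after PEA, where a missing day is least likely.
- A reader might infer that a post-operative PAH drug is lost from endpoint 11. The documents do not show this. Section 11 asks whether therapy occurs between PEA and Visit 4, so use continuing past PEA could count. PAH-targeted therapy is also assessed at Visits 3 and 4. What remains is that Section 8.3 names no deciding source.
- A reader might infer that such a drug removes the patient from the per-protocol set. Membership is settled at blind data review (SAP 4.3.3 and 5.2), and nothing says an imputed date decides it. The realistic effect is a query.
- V0-V4 contains both sides of surgery. V0-V3 already includes PEA to Visit 3, so only starts after Visit 3 could be wrongly drawn in. The composite runs from randomisation (SAP 8.2.2).

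None of this removes the gap for V0-V2. There a stated rule gives the wrong side of surgery for identifiable records, and no other text corrects it.

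**Conclusion.** The point holds as a minor one. SAP 13.4 has no PEA anchor. A post-PEA start with the day missing in the PEA month (unless PEA was on the 1st), or with day and month missing in most cases, is dated before surgery. Such AEs can enter the V0-V2 AE and special-interest summaries. A post-operative PAH drug can be misdated in the same way, with a possible but not demonstrated effect on exploratory endpoint 11 and on queries at the per-protocol review.

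The shares are conditional on a date being partial and on evenly spread timing. If events cluster early after surgery, the day-only share lies nearer the 0-7 day figure than the 0-180 day figure. The number of partial dates is unknown and probably small, and nothing in the documents suggests that it differs between the blinded arms. The primary endpoint, the composite, the V0-V4 window and the perioperative complications endpoint are unaffected.

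**What to change.** Before database lock:

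1. In SAP 13.4, keep the first-dose rule for treatment-emergent status. For windows that separate time before and after PEA, add a second rule. It applies when the known parts of a start date are compatible with both sides of PEA and the eCRF or source identifies the start as post-operative. The start is then the later of the imputed date and the PEA date. Otherwise the current rule stays.
2. List every imputed record whose possible dates span PEA for the blind data review.
3. In SAP 8.3, state that endpoint 11 counts any PAH-targeted therapy in use after PEA, from ongoing use or the Visit 3 or Visit 4 assessment, and not only therapy with an imputed start after PEA.

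The post-operative indication in step 1 is needed. Moving everything first reported at Visit 3 to the PEA date would push true starts between Visit 2 and PEA to after surgery, and the documents do not show that the visit of first report is stored for AEs or medications.

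The cost is a few lines of SAP text and program. Some ambiguity remains for starts between Visit 2 and PEA, a gap of at most a week.
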